Hypothesis 2b: SSRI use since stroke onset is associated with greater gains with all treatments in the subacute period, independently of depression. To test this hypothesis, we will collapse aphasic participants across treatment groups, and compare the primary outcome measures for aphasic participants who have continuously taken SSRIs to aphasic participants who have not taken SSRIs. If SSRI use enhances plasticity at the subacute stage, it might augment the effect of A-tDCS and SALT without tDCS. Therefore, we predict that A-tDCS or sham combined with SALT over 15 sessions will be associated with greater gains in accuracy in naming untrained pictures in APHASIC PARTICIPANTS who have been taking SSRIs continuously since stroke onset, compared to the identical interventions in APHASIC PARTICIPANTS who have not been taking SSRIs. APHASIC PARTICIPANTS who have taken SSRIs for only part of the time will not be included in the analysis. Based on a recent survey of the inpatient stroke service, we predict about 50% of participants (n=20) will have taken SSRIs continuously, and almost 50% (n=17-20) will not have been exposed to SSRIs since stroke. The adjusted mean change (95% CI) in naming accuracy on untrained stimuli from baseline to 1 week, 5 weeks, and 20 weeks post-treatment for the SSRI-treated and the SSRI-untreated groups will be estimated using a mixed effects model adjusting for treatment group, baseline naming accuracy, time (with week 1, 5, or 20 as a categorical variable and a random effect for subject), and any subject characteristic found to be important in the secondary analysis (age, education, time of initiation of treatment, previous SALT and lesion volume, and interactions with treatment). We will then evaluate the independent effects of SSRI use, depression (measured at each time point with Patient Health Questionnaire-9, PHQ-9, Williams et al., 2005), and tDCS versus sham on the primary outcome variable using a multiple regression. Although we may not have the power to detect a significant effect of SSRIs, a few studies with similar small numbers have reported significant effects of SSRIs on stroke recovery measured with less sensitive measures such as the mRS. The goal of this exploratory aim is to determine whether or not we need to control for SSRI use in a subsequent clinical trial of A-tDCS in subacute stroke.

Date: March 2, 2021

Principal Investigator: [name], MA

Application Number: IRB00089018

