Hypothesis 2b: To address the hypothesis that SSRI use since stroke onset is associated with greater gains with all treatments in the subacute period, independently of depression, we will collapse participants across treatment groups, and compare the primary outcome measures for participants who have continuously taken SSRIs to participants who have not taken SSRIs. If SSRI use enhances plasticity at the subacute stage, it might augment the effect of A-tDCS and naming therapy without tDCS. Participants who have taken SSRIs for only part of the time will not be included in the analysis. The adjusted mean change (95% CI) in naming accuracy on untrained stimuli from baseline to 1 week, 5 weeks, and 20 weeks post-treatment for the SSRI-treated and the SSRI-untreated groups will be estimated using a mixed effects model adjusting for treatment group, baseline naming accuracy, time (with week 1, 5, or 20 as a categorical variable and a random effect for subject), and any baseline subject characteristic found to be statistically significant in the primary or subgroup analyses. We will then evaluate the independent effects of SSRI use, depression (measured at each time point with PHQ-9 score of ≥ 15), and tDCS vs sham on the primary outcome graphically. Although we may not have the power to detect a significant effect of SSRIs, a few studies with similar small numbers have reported significant effects of SSRIs on stroke recovery measured with less sensitive measures such as the mRS. The goal of this exploratory aim is to determine whether or not we need to control for SSRI use in a subsequent clinical trial of A-tDCS in subacute stroke.

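### Hypothesis 2b claims an SSRI effect independent of depression, but the SAP swaps the protocol's regression for a graph and plans no depression-adjusted estimate

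*SAP*

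**What the plan says.** SAP Section 11 states the hypothesis as "SSRI use since stroke onset is associated with greater gains with all treatments in the subacute period, independently of depression". It plans two steps.

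- **Step 1** is a "mixed effects model adjusting for treatment group, baseline naming accuracy, time", and also for "any baseline subject characteristic found to be statistically significant in the primary or subgroup analyses". It gives adjusted mean change in untrained naming with 95% CI at weeks 1, 5 and 20, for continuous SSRI users and for participants never exposed. Participants with partial exposure are left out.
- **Step 2** takes up the independence claim. SSRI use and "depression (measured at each time point with PHQ-9 score of ≥ 15") are to be evaluated, "and tDCS vs sham on the primary outcome graphically".

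Protocol Section 2, Hypothesis 2b, has the same two steps, but the second differs. Depression there is "depression (measured at each time point with Patient Health Questionnaire-9, PHQ-9", with no cut-off, and its effect is evaluated together with SSRI use "and tDCS versus sham on the primary outcome variable using a multiple regression".

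SAP Section 2 says that the final SAP takes precedence over the protocol and that the SAP will be updated before database lock. Both documents call the aim exploratory, concede that power may be lacking, and say that it should show whether a later trial must control for SSRI use.

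**The concern.** SSRI use is not randomised here. Protocol Section 3 puts post-stroke depression at 30-60% and says that drug treatment reduces it, so the documents themselves link SSRI exposure with depression. A claim that the SSRI effect is independent of depression therefore needs an analysis with both variables in it. The protocol had one. The SAP keeps the claim and removes that analysis without giving a reason.

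A plot yields no adjusted SSRI estimate, no interval and no test. Followed as written, the SAP would leave the trial able to say whether SSRI users gained more, but not whether the difference remains once depression is taken into account. What is at stake is one clause of an exploratory hypothesis. The primary and secondary treatment comparisons are not affected.

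**Working it through.** **Does any planned SAP model hold both SSRI use and depression?**

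- Section 8.2, primary model: aphasia type, AQ and age. No depression.
- Section 11, subgroup factors: SSRI use, age, education, time since onset and lesion volume. No depression.
- Section 11, Hypothesis 2a models: arm, AQ, age, education and time since onset, then SSRI use. No depression.
- Section 11, Hypothesis 2b mixed model: arm, baseline naming, time and baseline characteristics selected by significance in the analyses above. Depression is not named.
- PHQ-9 otherwise appears as a row of the baseline table (Section 7) and as a secondary outcome (Section 10).

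So no specified model contains both.

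**The plan's own figure.** The documents give no figure for Hypothesis 2b. The one available for checking the inputs is the 89% power in SAP Section 8.3 (20 per group, difference 23, SD 22.2, two-sided alpha 0.05). The standard error is 22.2 × √(1/20 + 1/20) = 7.02, and the noncentrality is 23/7.02 = 3.28 on 38 df. The noncentral t gives 0.891, which reproduces the 89%.

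**Precision of an SSRI contrast.** The protocol expects 20 continuous users and 17-20 unexposed. With half-width = t(0.975) × 22.2 × √(1/n1 + 1/n2):

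- 20 vs 20: 2.024 × 7.02 = 14.2
- 20 vs 17: 2.030 × 7.32 = 14.9

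The difference detectable with 80% power is 20.2 and 21.1 respectively. These are simple two-group figures at one time point. Baseline adjustment could narrow the interval, and correlation between SSRI use and PHQ-9 would widen it. Reading 22.2 as items is itself an assumption: the plan takes the SD from a study whose gains Protocol Section 3 reports as percentages in auditory comprehension.

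**What the cut at 15 costs.** The documents do not give the share scoring 15 or more. For a normal score with upper share p and cut-point c, the information kept is φ(c)²/[p(1−p)].

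- p = 10%: φ(1.2816)²/0.09 = 0.34; about 4 of 40 participants, on average 1 per SSRI-by-arm cell
- p = 20%: 0.49; about 8 of 40, or 2 per cell
- p = 30%: 0.58; about 12 of 40, or 3 per cell

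A graph with 1 to 3 participants above the cut per cell could not show an independent effect of anything.

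**Illustrative size of bias if depression is left out.** All inputs except 22.2 are assumed, and PHQ-9 is treated as a pure confounder. Bias = d × r × 22.2, where d is the user/non-user gap in PHQ-9 (in SD) and r is the correlation of PHQ-9 with change.

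- Low: 0.3 × 0.2 × 22.2 = 1.3
- High: 0.8 × 0.3 × 22.2 = 5.3

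A simulation (n = 40, no true SSRI effect, latent SSRI-depression correlation 0.3 to 0.7, depression-outcome correlation −0.2 to −0.4, 10-30% above the cut) gave absolute bias of about 2 to 10 items unadjusted, about 1 to 7.5 with the binary cut in the model, and about 0 with the continuous score. The bias was negative only because depressed participants were assumed to be more often SSRI users and to improve less.

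**The case against.** The strongest replies are these.

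**The SAP still answers much of the question.** Step 1 gives an SSRI contrast with 95% CI at three time points. The stated goal, deciding whether a later trial must control for SSRI use, is largely prognostic: if users gain more or less for any reason, SSRI use is a candidate for stratification or adjustment. This stands. A reader might infer that Hypothesis 2b cannot be answered at all. The documents do not support that, because only the independence clause lacks an estimate.

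**Confounding is plausible but not shown.** Previous psychiatric disease is an exclusion (Protocol Section 5), although SAP Section 7 still tabulates a history of depression. Continuous users started their SSRI at stroke onset, before the first study PHQ-9 at Visit 2, so PHQ-9 may be partly a consequence of SSRI use. This stands, and it shapes the fix: an estimate adjusted for PHQ-9 is not simply the unadjusted one with confounding removed. A reader might also infer that the planned contrast is biased by several items in a known direction. The documents give neither the size nor the sign.

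**Imprecision dominates.** The illustrative 1.3-5.3 is about 9% (1.3/14.9) to 37% (5.3/14.2) of the CI half-width. This stands as a limit on importance, though an imprecise interval is still more informative than none.

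**PHQ-9 might enter the model anyway.** The subgroup list in Section 11 is open-ended, and PHQ-9 is a baseline variable. This is true, but selecting a confounder by its significance in about 40 people is not prespecified control for it.

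**The SAP may depart from the protocol.** It may, and the difference alone is not an error. The defect lies within the SAP: the hypothesis it states and the analysis it plans for that hypothesis do not match.

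**Conclusion.** The point holds for the clause on independence from depression. The SAP provides a depression-unadjusted SSRI contrast with 95% CI, and no estimate, interval or test for that clause. This follows from the text alone and needs no assumption.

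The graph in place of the regression is the main defect. The cut at 15 is secondary: it discards information, but in a regression it would not by itself leave the clause without an estimate. How much it discards depends on an assumed share above the cut.

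The consequence is limited. The aim is exploratory, admits low power, and would have a half-width of about 14-15 items at the plan's SD even after repair. The bias figures are illustrations resting on assumed correlations. The change is worth making because the SAP is to be updated before lock and the repair restores what the protocol already planned.

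**What to change.** In SAP Section 11, Hypothesis 2b:

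- Fit the mixed model, which already contains SSRI use and arm, without and with PHQ-9 as a continuous score, on the same participants. Report the SSRI effect with its 95% CI from both fits.
- State in advance which PHQ-9 is used, for example the Visit 2 baseline value, with time-varying PHQ-9 as a sensitivity analysis. If the time-varying version is kept, confirm a PHQ-9 at week 20: Protocol Section 4 lists Visits 2, 18 and 20 and a six-month point, but does not plainly name week 20.
- State that PHQ-9 is measured after SSRI exposure began in continuous users and may be partly a mediator, so the two estimates answer different questions and neither is a randomised comparison.
- Keep the graph as a supplement and drop the cut at 15 from the inference.

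The cost is one model term and one degree of freedom in the main fit, a few sentences of SAP text, and no new data for the baseline version, since PHQ-9 is already collected at Visit 2.

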12. SAFETY ANALYSES

All adverse events will be summarized in terms of frequency, severity and relatedness to the study intervention using the MedDRA code. All subjects who received at least one session of A-tDCS or S-tDCS will be included in the safety analysis. The cumulative incidences of adverse events will be compared between the treatment groups using Fisher's exact test at the two-sided alpha level of 0.05.

References

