After informed consent is received, a neurological examination will be performed and multiple screening assessments will be conducted including a tDCS and MRI safety screening (see below). If the participant passes the initial screening portion, speech and language diagnostic testing will be conducted during the same visit (Visit 1). During the next visit (Visit 2), participants will undergo a second baseline assessment of naming ability and assessment of connected speech. On that visit, participants who have no contraindication for MRI will be randomized to (1) fMRI electrode placement or (2) structural electrode placement. All participants who have no contraindication will have structural and rsfcMRI. Those randomized to fMRI electrode placement will also participate in the naming paradigm during the MRI. Participants may also undergo fNIRS at this visit. The third visit will include electrode positioning and tDCS treatment administration. Participants will receive 15 sessions (Visits 3-17) of tDCS + SALT administration. At the beginning of Visit 3, eligible participants will be randomized to receive either A-tDCS (1 mA) or sham-tDCS (placebo) for 15 sessions (20-minutes per each 45-minute behavioral treatment session) over the course of three weeks. A computer-delivered naming treatment will be coupled with the stimulation. The computer-delivered treatment task will be 45-minutes in total length, so that it will commence at the same time as the tDCS administration and continue for another 25-minutes after the tDCS has ceased. To assess cardiovascular arousal, blood pressure and heart rate will be measured before and after each session. Additionally, discomfort ratings will be recorded following the end of each session using the Wong-Baker FACES Pain Rating Scale (Wong & Baker, 1988) and a weekly neurological exam will be administered by a neurologist.

Neither the participant nor the clinician monitoring and setting up the treatment will have knowledge of the treatment condition (A-tDCS versus sham).

Date: March 2, 2021

Principal Investigator: [name], MA

Application Number: IRB00089018

Utilizing a computerized picture naming assessment (PNT), all participants will be assessed at several different time points throughout the experiment: twice immediately before and twice the week immediately following the fifteenth and final treatment session; twice at five weeks follow-up after the end of treatment; and twice at 20 weeks after the end of treatment.

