Date: March 2, 2021

Principal Investigator: [name], MA

Application Number: IRB00089018

post-testing in secondary outcome measures will be reported by treatment group along with the 95% confidence intervals. Treatment comparisons will be made with a paired t- test. For binary variables, the proportion of subjects immediately post-testing will be reported by treatment group along with the 95% confidence intervals.

Post-Testing Phase

The longer follow-up post-testing phase will provide exploratory information on whether the immediate post-testing improvement after three weeks of treatment can be sustained. The mean (95% CI) changes from baseline to immediate (within one week) post-testing, five weeks (after the end of treatment) post-testing and 20 weeks (after the end of treatment) post-testing will be reported. Box and whisker plots will be produced to show the distribution of naming accuracy over time by treatment group. To explore the longitudinal data, a general linear mixed model (GLMM) will be constructed by tDCS group for the dependent variable (anomia). The GLMM will incorporate random subject effects to account for repeated measurements being made on subjects; the model will include time, aphasia type, severity, and clinical center as independent variables. A similar modeling approach may be applied to other secondary outcomes.

Safety Analyses

All adverse experiences will be summarized in terms of frequency, severity and relatedness to the study treatment using the MedDRA code. All subjects who received tDCS will be included in the safety analysis. At the end of the study, the cumulative incidences of adverse events are compared between the two treatment groups using Fisher's exact test at the two-sided alpha level of 0.05.

The repeated measures of the FACES pain rating scale will be compared by treatment group by fitting a repeated measures proportional odds model.

DSMB Reporting

The study biostatistician will generate closed and open DSMB reports semi-annually or more frequently, as determined by the DSMB. Each DSMB report provides cumulative summary statistics on enrollment; subject status in the study (e.g., number completed study, drop outs, etc.); baseline characteristics; safety data, including AEs and SAEs; and data quality information. The statistics for the closed DSMB Reports are provided by treatment group displayed as A or B. The open report contains aggregated statistics only, i.e., not by treatment group.

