d. Early stopping rules. N/A

8. Risks

a. Medical risks, listing all procedures, their major and minor risks and expected frequency.

tDCS

The present study involves application of transcranial direct current stimulation. Weak direct currents can be applied non-invasively, transcranially and painlessly (Nitsche et al., 2003; Priori et al., 2009). This is a non-invasive and painless technique that leads to transient changes in cortical excitability that are fully reversible (Nitsche et al., 2002). There are no known risks of tDCS to other than mild local discomfort at the electrode sites (much less than TMS for example). Several published studies on humans (Boggio et al., 2009; Gandiga et al., 2006; Hummel et al., 2005; Nitsche et al., 2003; 2004; Paulus, 2003; Uy & Ridding, 2003) reported the following objective safety data:

Date: March 2, 2021

Principal Investigator: [name], MA

Application Number: IRB00089018

- No heating of electrodes
- No demonstrable changes in the skin underlying electrode placement after a stimulation period similar to the one proposed in this protocol.
- Mild itching sensation in the absence of pain that never led to stopping a study.
- No change in serum neuron-specific enolase (NSE, marker for neuronal damage) in 5 participants immediately and 1 hour after exposure to 13 min of 1 mA anodal tDCS to motor cortex
- No changes in diffusion weighted or contrast-enhanced MRI and in EEG after exposure to tDCS (Nitsche et al., 2004).

Two reports, one evaluating the safety of tDCS applied in different brain regions in 102 healthy and stroke individuals (Poreisz et al., 2007) and another one investigating the safety of different forms and intensities of tDCS in 103 healthy participants (Iyer et al., 2005), concluded that tDCS is safe and only associated with relatively minor adverse effects in healthy and participants with different neurological conditions. In addition, a double-blind sham-controlled study has shown that comparing tDCS and sham stimulation of the motor cortex elicited minimal discomfort and difference in the duration of tingling sensations. There were no differences in self-rated attention or fatigue, and the study participants or investigators could not distinguish real tDCS from sham (Gandiga et al., 2006). Taken together, all available research suggests that prolonged application should not pose a risk of brain damage when applied according to safety guidelines.

MRI

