2. STATISTICAL ANALYSIS PLAN AND STATISTICAL REPORTS

This document provides the details of the statistical analyses planned for the trial. Prior to locking the database and breaking the code, this Statistical Analysis Plan (SAP) will be updated. The final SAP will define all “pre-specified, pre-planned analyses” and will trump the protocol.

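### SAP section 12 leaves out the protocol's planned FACES comparison by arm, so the measure of the one named tDCS risk has no pre-specified analysis

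*SAP*

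**What the plan says.** **The risk.** Protocol section 8a (Medical risks, tDCS) recognises no risk of tDCS "other than mild local discomfort at the electrode sites".

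**The measure.** Protocol section 4a (Study Procedures Overview) says "discomfort ratings will be recorded following the end of each session using the Wong-Baker FACES Pain Rating Scale". Under Procedures for Treatment, adverse-event logging is step 12 and the FACES rating is step 13, so they are separate entries. Participants have 15 treatment sessions.

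**The protocol's analysis.** Protocol section 7c (Safety Analyses) has three parts: a MedDRA-coded adverse-event summary, Fisher's exact test on cumulative incidence by arm, and a third: "The repeated measures of the FACES pain rating scale will be compared by treatment group by fitting a repeated measures proportional odds model".

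**The SAP's analysis.** SAP section 12 has the first two parts only: "All adverse events will be summarized in terms of frequency, severity and relatedness to the study intervention using the MedDRA code", followed by Fisher's exact test at two-sided 0.05.

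**Precedence and status.** SAP section 2 says the final SAP will define every pre-planned analysis "and will trump the protocol". It also says "Prior to locking the database and breaking the code, this Statistical Analysis Plan (SAP) will be updated".

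**The concern.** SAP section 12 follows the protocol's safety text closely for two of its three parts and stops before the third. Nothing records a decision to drop the FACES model, so it looks like an oversight. Because the final SAP governs, an oversight carried into it would take away the pre-specified status of the one analysis aimed at the one harm the protocol names.

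What is at stake is the quality of the tolerability report. Protocol section 7c says a rejected null would lead the sponsor to consider a Phase III study. Anyone planning that study would want to know how discomfort compared between active and sham sessions in people within three months of a stroke. Without the FACES model, the planned arm comparison sees discomfort only through adverse-event entries, which depend on someone judging it worth logging. An analysis of the ratings added after unblinding would be post hoc.

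**Working it through.** The plan gives no figure for its safety analyses, so there is none to reproduce. The check is a comparison of texts, with a count for scale.

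**1. Safety analyses side by side**

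| Element | Protocol 7c | SAP 12 |
|---|---|---|
| Adverse events by frequency, severity, relatedness | yes | yes |
| Fisher's exact test by arm, two-sided 0.05 | yes | yes |
| FACES, repeated-measures proportional odds by arm | yes | absent |

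**2. Is FACES elsewhere in the SAP?** No. It is not in the acronym list (section 1), the baseline table (section 7), the primary or sensitivity analyses (section 8), the secondary outcomes (section 10) or the exploratory analyses (section 11).

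**3. Could adverse-event reporting stand in for it?** Only in part. The two are separate steps after each session, and neither document has a rule that turns a FACES score into an adverse event. A cumulative-incidence comparison also reduces up to 15 ordinal ratings per person to whether an event was ever logged.

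**4. How much data is affected?** Ratings = participants × sessions, with 15 sessions each (Protocol 4a). Protocol 7c expects 50 enrolled and 40 to 45 completing.

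- 40 × 15 = 600
- 45 × 15 = 675
- 50 × 15 = 750

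With 1:1 allocation that is 300 to 375 per arm. These counts assume full attendance. SAP section 4 aims for 50 randomised participants with a 1-week PNT, so more than 50 could be randomised and 750 is not a strict ceiling. Ratings are clustered within people, so the independent units remain the 40 to 50 participants.

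**5. How sensitive is the test that remains?** The documents give no event rates, so the rates below are assumptions. Exact power of Fisher's test at two-sided 0.05:

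| Assumed rates, one arm vs the other | 20 per arm | 25 per arm |
|---|---|---|
| 30% vs 10% | 24% | 31% |
| 50% vs 20% | 41% | 51% |
| 40% vs 10% | 49% | 59% |
| 60% vs 20% | 65% | 79% |
| 50% vs 10% | 74% | 83% |

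Only large differences in logged events would be likely to show. This is background, and the finding does not depend on it.

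**The case against.** The strongest reply is that this is silence in an unfinished document. Precedence belongs to the final SAP, an update before lock is promised, and nothing withdraws the FACES model. That stands, and it is why the point is conditional on section 12 being finalised as written. The documents do not show whether this version is the final one.

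The reply can add that neither the primary test nor its alpha and power is touched, and that no stated objective concerns tolerability. That also stands and limits the weight of the point.

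Three stronger readings are tempting, and the documents do not support them.

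- **That the SAP also dropped a blood pressure and heart rate analysis.** It did not. Protocol 4a says "To assess cardiovascular arousal, blood pressure and heart rate will be measured before and after each session", but the protocol never planned an analysis of these readings, and their purpose is not electrode-site discomfort. Asking for a summary is asking for an addition.
- **That discomfort or a cardiovascular response would not be reported at all.** Staff log adverse events after every session. Protocol 8c requires all of them to be recorded and sent to the IRB and DSMB whatever their intensity or cause. SAP 12 then compares arms, and the safety data in the DSMB reports are not limited to adverse events. What lacks a planned summary is change that nobody logs as an adverse event.
- **That FACES by arm would test the blinding.** The rating follows a 45-minute session in which stimulation stops at 20 minutes, so it comes about 45 − 20 = 25 minutes after the current ends. It is poor evidence of whether active and sham felt different.

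The same delay may blunt FACES as a record of discomfort during stimulation. It is still the discomfort measure the trial collects and the one the protocol chose to model.

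**Conclusion.** The point holds in a limited form. The protocol pre-specifies a FACES comparison by arm, the SAP omits it without a stated reason, and the SAP claims precedence once final. If section 12 is finalised unchanged, about 600 to 750 ratings (40 to 50 participants, full attendance) have no pre-specified analysis, and discomfort reaches the arm comparison only through logged adverse events.

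This is a gap in safety reporting that should be closed. It does not bias the efficacy result. The verdict rests on the text of the two documents and on the assumption that the pending update does not already restore the model.

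**What to change.** At the SAP update before database lock, add to section 12 the protocol's repeated-measures proportional odds model for FACES by arm:

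- use the safety sample of SAP section 5.4;
- state how repeated ratings within a participant are handled, which the protocol leaves open beyond calling the model repeated-measures;
- report the arm odds ratio with a 95% CI.

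If the sponsor meant to drop the model, section 12 should say so and give the reason.

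The cost is a few sentences and one extra safety table from data already collected. Sample size, alpha and the primary analysis do not change.

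Optional and separate: a descriptive by-arm table of pre-to-post session change in blood pressure and heart rate, since these are collected for a stated purpose and neither document summarises them. No model or threshold is needed for that.
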